1.2. Schema

Figure 1: Schematic Overview of the Main Study

Abbreviations: DBL=database lock; IV=intravenous; N=number of participants; PE=primary endpoint; R=randomization; SC=subcutaneous; SE=secondary endpoints

Figure 2: Schematic Overview of LTE

Abbreviations: DBL=database lock; IV=intravenous; N=number of participants; PE=primary endpoint; R=randomization; SC=subcutaneous; SE=secondary endpoints

1.3. Schedule of Activities (SoA)

Table 1: Schedule of Activities (SoA) of Screening and Double-Blind Study Intervention (Main Study)

Period	Screening	Double-blind Study Intervention														Safety Follow-up (EOS) °	Early Termination Visit (ET)
Week ^h	-6 to 0	0	4	8	12	16	20	24	28	32	36	40	44	48	52 ⁿ	60	
Study Procedure																	
Screening/Administrative																	
ICF ^a	X																
ICF for optional genetic research	X																
samples																	
ICF for participation of LTE ^p														(X)			
Medical history and demographics	X																
Inclusion/exclusion criteria ^b	X	X															
Study Intervention																	
Administration																	
Randomization		X															
Administer study intervention		X	X	X	X	X	X	X	X	X	X	X	X	X			
Efficacy Assessments ^c																	
mRSS ^g	X	X	X	X	X	X	X	X	X	X	X	X	X	X	X		X
Physician's global assessment		X			X			X			X				X		X
Digital ulcer assessment	X	X	X	X	X	X	X	X	X	X	X	X	X	X	X		X
Patient's global assessment		X			X			X			X				X		X
HAQ-DI		X			X			X			X				X		X
FSSG		X			X			X			X				X		X
Nailfold capillaroscopy		X						X							X		X
Lung HRCT (centrally read) ¹	X							X							X		
Pulmonary function tests ⁱ	X				X			X							X		X
ACR CRISS ^m	X				X			X							X		X
Safety Assessments																	
Physical examination	X	X	X	X	X	X	X	X	X	X	X	X	X	X	X	X	X
Height	X																
Weight	X				X			X							X		X
Vital signs	X	X	X	X	X	X	X	X	X	X	X	X	X	X	X	X	X
Tuberculosis evaluation ^k	X	X	X	X	X	X	X	X	X	X	X	X	X	X	X	X	X
12-lead ECG	X							X							X		X
Urine pregnancy test	X	X	X	X	X	X	X	X	X	X	X	X	X	X	X	X	X

 $CONFIDENTIAL-FOIA\ Exemptions\ Apply\ in\ U.S.$

Period	Screening	Screening Double-blind Study Intervention														Safety Follow-up (EOS) °	Early Termination Visit (ET)
Week ^h	-6 to 0	0	4	8	12	16	20	24	28	32	36	40	44	48	52 ⁿ	60	
Study Procedure																	
Chest radiograph	X																
Concomitant therapy	X	X	X	X	X	X	X	X	X	X	X	X	X	X	X	X	X
Adverse Events	X	X	X	X	X	X	X	X	X	X	X	X	X	X	X	X	X
Clinical Laboratory Tests																	
IGRA (QuantiFERON- TB test or T-SPOT)	X																
Hepatitis B and C serologye	X																
HIV antibody test	X																
Hematology	X	X	X	X	X	X	X	X	X	X	X	X	X	X	X	X	X
Chemistry including CRP	X	X	X	X	X	X	X	X	X	X	X	X	X	X	X	X	X
Urinalysis	X	X	X	X	X	X	X	X	X	X	X	X	X	X	X	X	X
Autoantibodies (including, but not limited to anti-RNA polymerase, anti-centromere, and anti-topoisomerase)	X																
Pharmacokinetics and																	
Immunogenicity																	
Serum guselkumab concentrationf		2X	2X	2X	X	X	X	X	X	X	X	X	X	X	X	X	X
Antibodies to guselkumab		X	X	X	X			X		X		X		X	X	X	X
Biomarkers																	
Serum biomarkers		X	X		X	X		X	X					X			X
PBMCs		X	X					X						X			X
Skin biopsy (optional)		X						X									
Pharmacogenomics (optional) ^d																	
Blood sample collection for DNA (EDTA tube)		X															
Blood sample collection for RNA (PAXgene tube)		X	X					X									

Abbreviations: CRP=C-reactive protein; DNA=deoxyribonucleic acid; ECG=electrocardiogram; EDTA= ethylenediaminetetraacetic acid; EOS= end-of-study; ET=early termination; FSSG= Frequency Scale for the Symptoms of Gastroesophageal reflux disease; HAQ-DI= Health Assessment Questionnaire-Disability Index; HIV= human immunodeficiency virus; HRCT= high resolution computed tomography; ICF=informed consent form; IGRA= interferon gamma release assays; LTE=

long-term extension, mRSS= modified Rodnan skin score; PBMC= Peripheral blood mononuclear cells; PRO=patient-reported outcome; RNA=ribonucleic acid; SoA=schedule of assessments

Footnotes:

- a. Must be signed before first study-related activity.
- b. Minimum criteria for the availability of documentation supporting the eligibility criteria will be described in the full protocol. Check clinical status again before first dose of study medication.
- c. All PRO assessments should be conducted before other assessments in the order listed in the above SoA table.
- d. The pharmacogenomic sample should be collected at the specified time points, but it may be collected at a later time point without constituting a protocol deviation.
- e. For participants who are eligible with surface antigen (HbsAg) negative, core antibody (anti-HBc) and/or surface antibody (anti-HBs) positive, and HBV DNA test is negative, HBV DNA quantitation should be monitored at least every 3 months or shorter.
- f. For all visits where study intervention will be administered, 1 blood sample should be collected prior to study intervention administration for evaluation of serum concentrations and/or antibodies to study intervention. In addition, for IV infusion-related visits (Week 0, 4, 8), another blood draw should be taken approximately 60 minutes after the completion of the IV infusion for serum concentration measurement.
- g. mRSS must be assessed by the same investigator longitudinally throughout the study
- h. Screening should occur within 6 weeks prior to W0 visit. The study visit week are indicated and calculated based on the day of randomization/first administration of the study intervention (W0 visit). Visit window should be ±7 days for each visit (Visit window for W0 visit should be -7 days).
- i. Pulmonary function tests include forced vital capacity (FVC) and diffusing capacity of the lung for carbon monoxide (DLCO). If decline in % predicted FVC ≥ 15 % (relative) is seen, another FVC test needs to be performed within a month.
- j. To be measured at a central laboratory
- k. Participants with potential active tuberculosis need to pause the study intervention administration until the tuberculosis assessment is completed.
- 1. For participants with stent, HRCT cannot be centrally read.
- m. For screening, information on ACR CRISS step 1 will be collected as SSc Condition of Interest.
- n. For participants who will NOT enter LTE, refer to Week 52 in Table 1. For participants who will enter LTE, refer to Week 52 and the subsequent visits in Table 2.
- o. Only participants who will NOT enter LTE should perform the safety follow up visit at Week 60.
- p. ICF for participation of LTE should be obtained at the latest at Week 52.

Table 2: Long-Term Extension for Eligible Participants Who Have Completed the Main Study (LTE)

Period		Long-term extension (LTE)									Safety Follow-up (LTE- EOS)	Early Termination Visit (LTE- ET)				
LTE Week ^a	52	56	60	64	68	72	76	80	84	88	92	96	100	104	112	
Study Procedure																
Administrative																
ICF for participation of LTE ^b	(X)															
Study Intervention Administration																
Administer study intervention ^c	X	X	X	X	X	X	X	X	X	X	X	X	X			
Training for self-administration ^d		X	X	X				**********				···>				
(Optional)																
At-home administration ^e (Optional)									X		X		X			
Efficacy Assessmentsf																
mRSS ^g	X	X	X	X	X	X	X	X		X		X		X		X
Physician's global assessment	X			X			X			X				X		X
Digital ulcer assessment	X			X			X			X				X		X
Patient's global assessment	X			X			X			X				X		X
HAQ-DI	X			X			X			X				X		X
FSSG	X			X			X			X				X		X
Nailfold capillaroscopy	X															
Lung HRCT (centrally read)h	X						X							X		
Pulmonary function tests ⁱ	X			X			X							X		X
ACR CRISS	X			X			X							X		X
Safety Assessments ^j																
Physical examination	X	X	X	X	X	X	X	X		X		X		X	X	X
Weight	X			X			X							X		X
Vital signs	X	X	X	X	X	X	X	X		X		X		X	X	X
Tuberculosis evaluationk	X	X	X	X	X	X	X	X		X		X		X	X	X
12-lead ECG	X						X							X		X
Urine pregnancy test	X	X	X	X	X	X	X	X		X		X		X	X	X
Concomitant therapyl	X	X	X	X	X	X	X	X	}	> X		> X		- 1	X	X
Adverse Events ¹	X	X	X	X	X	X	X	X	}	> X		> X		> X	X	X
Clinical Laboratory Tests																
Hematology	X	X	X	X	X	X	X	X		X		X		X	X	X
Chemistry including CRP	X	X	X	X	X	X	X	X		X		X		X	X	X

 $CONFIDENTIAL-FOIA\ Exemptions\ Apply\ in\ U.S.$

Period		Long-term extension (LTE)											Safety Follow-up (LTE- EOS)	Early Termination Visit (LTE- ET)		
LTE Week ^a	52	56	60	64	68	72	76	80	84	88	92	96	100	104	112	
Study Procedure																
Urinalysis	X	X	X	X	X	X	X	X		X		X		X	X	X
Pharmacokinetics and																
Immunogenicity																
Serum guselkumab concentration ^m	X	X	X	X			X			X		X		X	X	X
Antibodies to guselkumab	X	X	X	X			X			X		X		X	X	X

Abbreviations: CRP=C-reactive protein; DNA=deoxyribonucleic acid; ECG=electrocardiogram; EOS= end-of-study; ET=early termination; FSSG= Frequency Scale for the Symptoms of Gastroesophageal reflux disease; HAQ-DI= Health Assessment Questionnaire-Disability Index; HIV= human immunodeficiency virus; HRCT= high resolution computed tomography; ICF=informed consent form; LTE= long-term extension; mRSS= modified Rodnan skin score; PRO=patient-reported outcome; SoA=schedule of assessments

Footnotes:

- a. Visit window should be ± 7 days for each visit.
- b. IC for participation of LTE should be obtained at least the first assessments at Week 52.
- c. Self-administration can begin from LTE Week 68 visit according to the regional/local regulations and instruction at the discretion of the investigator and participant, and upon completion of 3 times training.
- d. Three times trainings are required prior to begin self-administration, and participants can start the training at any time after Week 56.
- e. For study participants who are trained to self-inject at home, study participants will be trained to perform self-evaluation for injection-site reactions and reporting of AEs after administering the study intervention at home. Participants will also be instructed to contact the investigator promptly in the event of any signs of an allergic reaction, infection, or bleeding. Participants will record all at-home study intervention administrations on a diary card.
- f. All PRO assessments should be conducted in the order listed in the above SoA table.
- g. mRSS must be assessed by the same investigator longitudinally throughout the study.
- h. For participants with stent, HRCT cannot be centrally read.
- i. Pulmonary function tests include forced vital capacity (FVC) and diffusing capacity of the lung for carbon monoxide (DLCO). If decline in FVC% predicted ≥15% (relative) is seen, another FVC test needs to be performed within a month.
- j. For participants who are eligible with surface antigen (HbsAg) negative, core antibody (anti-HBc) and/or surface antibody (anti-HBs) positive, and HBV DNA test is negative, HBV DNA quantitation should be monitored at least every 3 months or shorter.
- k. Participants with potential active tuberculosis need to pause the study intervention administration until the tuberculosis assessment is completed.
- I. If participants come to the clinical site for study intervention at following visits; LTE Week 84, 92 and 100, site staff should confirm if there is any change of concomitant therapies and adverse events. If necessary, safety assessments and clinical laboratory test can be performed as an unscheduled assessment.
- m. 1 blood sample should be collected prior to study intervention administration for evaluation of serum concentrations and/or antibodies to study intervention.

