	•	Change from baseline in Patient global assessment (PGA) at Week 24 and Week 52
	•	Change from baseline in Physician global assessment (PhGA) at Week 24 and Week 52
To evaluate the long-term efficacy of guselkumab in participant with SSc	•	Change from baseline and Week 52 in mRSS at Week 76 and Week 104
	•	The proportion of participants who experience worsening of mRSS at Week 76 and Week 104
	•	The proportion of participants achieving a score of 0.6 in American College of Rheumatology Combined Response Index in dcSSc (ACR CRISS) at Week 76 and Week 104
	•	Change from baseline in forced vital capacity (FVC) and percent predicted FVC at Week 76 and Week 104
	•	The proportion of participants who experience worsening of FVC at Week 76 and Week 104
	•	Change from baseline in the measured absolute diffusing capacity of the lung for carbon monoxide (DLCO) and the derived percent predicted DLCO at Week 76 and Week 104
	•	Change from baseline in Health Assessment Questionnaire-Disability Index (HAQ-DI) score at Week 76 and Week 104
	•	Change from baseline in digital ulcer counts at Week 76 and Week 104
	•	Change from baseline in fibrotic change assessed with high-resolution computed tomography (HRCT) at Week 76 and Week 104 in participants with baseline fibrosis/fibrotic changes
	•	The proportion of participants who experience worsening of fibrotic change assessed with HRCT at Week 76 and Week 104

Objectives	Endpoints
	• Change from baseline in Frequency Scale for the Symptoms of Gastroesophageal reflux disease (FSSG) score at Week 76 and Week 104
To evaluate the effect of guselkumab vs placebo on the pharmacodynamic (PD) and SSc disease biomarkers	• Change from baseline levels of skin (optional) and circulating (blood based) biomarkers over time to enable:
	Evaluation of target engagement in tissue/efficacy pharmacodynamic (PD) readouts
	• Single nucleotide polymorphisms (SNPs) frequency associated with IL-23 pathway

Refer to Section 8, STUDY ASSESSMENTS AND PROCEDURES for evaluations related to endpoints.

HYPOTHESIS

This is a PoC study aimed at detecting an early efficacy signal of guselkumab in participants with SSc, compared to placebo, to support further clinical development.

- The null hypothesis is that the treatment difference between guselkumab and placebo for the primary endpoint is 0.
- The alternative hypothesis is that the treatment difference between guselkumab and placebo for the primary endpoint is $\neq 0$.

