8. STUDY ASSESSMENTS AND PROCEDURES

Overview

The Schedule of Activities summarizes the frequency and timing of efficacy, PK, immunogenicity, PD, biomarker, pharmacogenomic, and safety measurements applicable to this study.

If multiple assessments are scheduled for the same timepoint, it is recommended that procedures be performed in the following sequence: ECG and vital signs (blood pressure, pulse rate, respiratory rate, and axillary body temperature) should be performed first, and then blood draws for PK or laboratory measurements. Urine and blood collections for PK and PD assessments should be kept as close to the specified time as possible. Other measurements may be done earlier than specified timepoints if needed. Actual dates and times of assessments will be recorded in the source documentation and eCRF.

For each participant, the maximum amount of blood drawn in this study will not exceed 567 mL through Week 112.

Repeat or unscheduled samples may be taken for safety reasons or for technical issues with the samples.

Table 3: Volume of Blood to be Collected from Each Participant

	** 1	N. 66 1	Approximate
	Volume per	No. of Samples	Total Volume of
Type of Sample	Sample (mL)	per Participant	Blood (mL) ^a
Safety (including screening and post-intervention			
assessments)			
- T-spot	10	1	10
- Hematology	2 - 3	26	52 - 78
- Serum chemistry	2.5	26	65
- Serology (HIV, HBV, HCV)	8.5	1	8.5
- HBV DNA testing	6	8	48
Pharmacokinetic/Immunogenicity samples	7.5	25	187.5
Pharmacodynamic/Biomarker samples			
- PBMCs	2×8	4	64
- Serum biomarkers	8.5	7	59.5
Autoantibodies	3	1	3
Pharmacogenomic sample ^b			
- EDTA	4 - 6	1	4 - 6
- Paxgene tube	5	3	15
Approximate Total ^c			516.5 – 544.5

Abbreviations: DNA=deoxyribonucleic acid; EDTA= ethylenediaminetetraacetic acid; HBV= hepatitis B virus; HCV= hepatitis C virus; HIV= human immunodeficiency virus; PBMC= peripheral blood mononuclear cells

a. Calculated as number of samples multiplied by amount of blood per sample.

b. A blood sample will be collected only from participants who have consented to provide an optional DNA and RNA samples for research.

c. Repeat or unscheduled samples may be taken for safety reasons or technical issues with the samples.

Screening

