Serum will be collected from all subjects to assess PD markers associated with guselkumab as well as markers related to SSc. Measurements may include but are not limited to serum levels of IL-17A, IL-17F, IL-22, beta defensin-2 (BD-2), and SAA. The samples will be collected at Weeks 0, 4, 12, 16, 24, 28, and 48 and analyzed by immunoassays. Broader proteomic profiling (eg, via Olink method) for biomarker discovery may be performed. Additionally, serum samples should also be collected at the final visit from participants who discontinued study intervention or were withdrawn from the study.

Blood samples for the isolation of PBMCs will also be collected for subsequent immunophenotyping analyses by multiparameter flow cytometry or mass cytometry (CyTOF) analysis to measure immune cell populations before and during treatment. The samples will be collected at Weeks 0, 4, 24, and 48. Gene expression analysis may also be performed; this may include single cell RNA-seq profiling. Additionally, serum samples for isolation of PBMCs should also be collected at the final visit from participants who discontinued study intervention or were withdrawn from the study

Results of pharmacodynamic/biomarker analyses will be presented in a separate report.

Pharmacokinetic/Pharmacodynamic Analyses

The relationship between serum concentrations of guselkumab and the efficacy measures and/or relevant PD endpoints, including biomarkers in blood or in skin biopsies, may be explored graphically when appropriate. If any visual trend is observed, additional analysis may be conducted if deemed necessary.

Pharmacogenomic Analyses

Genetic analysis may help to identify population subgroups that respond differently to a drug. A single DNA sample at Week 0 as specified in the SoA (Section 1.3) will be used to explore genetic factors that may influence molecular effects, clinical efficacy, or tolerability of guselkumab and to identify genetic factors associated with SSc. A locus of interest is the *IL12RB1* gene; a reported SSc risk allele has been identified in this gene and there is potential association with expression of the gene product (encoding a receptor for IL-23). Analysis applied to DNA samples may focus on genotyping, using molecular arrays to scan polymorphisms across the genome. Participation in the DNA sampling is optional.

Results will be presented in a separate report.

Interim Analysis

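### Footnote d to the Schedule of Activities excuses late collection of the RNA tubes as well as the DNA tube, so a Week 0 RNA sample may be post-dose without being a deviation

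*Protocol*

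**What the plan says.** - **The waiver.** In Protocol 1.3, Table 1, the marker for footnote d sits on the block heading, "Pharmacogenomics (optional) ^d". The footnote asks for collection at the scheduled points but adds that "it may be collected at a later time point without constituting a protocol deviation". It gives no latest time and does not separate DNA from RNA.
- **What the block contains.** There are two rows: an EDTA tube for DNA at Week 0, and a row beginning "Blood sample collection for RNA (PAXgene tube" that is marked at Weeks 0, 4 and 24.
- **Table 3 (Protocol 8).** The EDTA and PAXgene tubes are both listed under the pharmacogenomic sample, with the note "A blood sample will be collected only from participants who have consented to provide an optional DNA and RNA samples for research".
- **The pre-dose rule.** Footnote f to Table 1 says that "1 blood sample should be collected prior to study intervention administration for evaluation of serum concentrations and/or antibodies to study intervention". RNA is not named.
- **The endpoint.** Protocol 3 lists, as exploratory, "Change from baseline levels of skin (optional) and circulating (blood based) biomarkers over time to enable" an evaluation of target engagement and pharmacodynamic readouts, under an objective that compares guselkumab with placebo.

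**The concern.** Germline DNA does not change with treatment, so a waiver for a late DNA tube is sensible. RNA is different. A tube scheduled at three visits is presumably meant to show expression over time, and the Week 0 tube is the only one of the three that can be taken before treatment. Once the first dose has been given, that sample cannot be recovered.

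At stake is the meaning of any change from baseline computed from these tubes. A post-dose Week 0 tube may already contain part of the drug's effect in guselkumab participants, and can contain none in placebo participants. Subtracting it would then remove real effect from one arm only.

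**Working it through.** No statistical figure in the plan bears on this point, so the check is a reading of the relevant places side by side, plus one count.

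**1. Does footnote d reach RNA?** The marker is on the heading above both rows. Table 1 has three RNA time points (Weeks 0, 4, 24). Table 3 has three PAXgene samples of 5 mL, and 3 × 5 mL = 15 mL, which is the total it prints, under the pharmacogenomic heading. The two tables agree, so as written the RNA tubes are part of the sample that the footnote excuses.

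**2. Is Week 0 a dosing visit?** Yes. Table 1 marks administration at Weeks 0, 4 and 24, and footnote h ties Week 0 to randomization and first administration. A Week 0 tube drawn later in the visit than the dose, or at a later visit, is therefore post-dose.

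**3. Does another rule require the RNA tube before the dose?**
- Footnote f is confined to serum concentration and antibodies.
- Protocol 8 says "Urine and blood collections for PK and PD assessments should be kept as close to the specified time as possible". For the RNA tube, Table 1 specifies only a week, so this does not fix the order of draw and dose.
- Protocol 9.4.6 gives serum biomarker timing by week only: "The samples will be collected at Weeks 0, 4, 12, 16, 24, 28, and 48 and analyzed by immunoassays". SAP 5.8.3 repeats it.
- Neither document defines a biomarker baseline or excludes a post-dose Week 0 sample.

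**4. What is the RNA used for?** The pharmacogenomic analysis in Protocol 9.4.6 describes genotyping of a single DNA sample. Gene expression is named there for skin biopsies and in the text on PBMCs. No analysis of the PAXgene tubes is written. Their use for the blood biomarker endpoint is inferred from the repeated schedule.

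**5. Direction and size if so used.** Let *E* be the true mean drug effect on expression at Week 4 or 24. Let *p* be the share of guselkumab participants with RNA data whose Week 0 tube is post-dose, and *f* the fraction of *E* already present in that tube. Unaffected participants show *E* and affected ones show (1 − *f*)*E*, so the arm mean is

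(1 − *p*)*E* + *p*(1 − *f*)*E* = (1 − *pf*)*E*.

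The placebo arm has no corresponding drug effect to subtract. For *f* between 0 and 1 the comparison shrinks towards no difference. With *p* = 0 or *f* = 0 there is no bias. The documents give neither *p* nor *f*.

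**The case against.** The strongest case against the point is that it concerns an optional sample in exploratory work, that no PAXgene analysis is described, and that the laboratory manual supplied to sites (Protocol 8) may already require the Week 0 tube before dosing. Results go to a separate report, where a baseline could be defined. All of this stands as a limit on importance. It does not remove the footnote, which expressly excuses late collection and makes no exception for RNA.

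A reader might infer more than the documents support:

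- **That affected samples could not be found later.** Protocol 8 requires actual collection dates and times to be recorded, and Protocol 6.4 requires infusion start and stop times. Comparing them identifies every post-dose Week 0 tube. What is missing is a rule that acts on the comparison.
- **That post-dose draws are likely.** Footnote f already requires a pre-dose draw at every dosing visit, so convenience favours pre-dose RNA collection at least as much as the extra draw after the infusion favours the reverse.
- **That the same harm arises at Weeks 4 and 24.** Those tubes are on treatment whichever side of the dose they fall.
- **That the effect would shrink by 10–20%.** This needs an assumed late rate of *p* = 10–20% and also *f* = 1, which gives factors of 0.90 to 0.80. With *f* = 0 the factor is 1.00. Nothing in the documents supports that late rate, or a full effect shortly after infusion. The corresponding head count, 28 × 0.10 = 2.8 to 28 × 0.20 = 5.6, treats every participant in the arm as consenting to an optional sample.
- **That serum biomarkers, PBMCs and skin biopsies are also excused.** They sit in a separate block of Table 1 without footnote d. For them the protocol merely leaves the pre-dose instruction unwritten. The purpose stated for the PBMC samples in Protocol 9.4.6 implies a pre-treatment Week 0 sample, and the laboratory and biopsy manuals may say so.

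**Conclusion.** The point holds for the optional RNA tubes. A stated rule, not just an omission, allows the only pre-treatment RNA sample to be taken after the first dose with no deviation. The consequence is conditional. It requires that the PAXgene tubes be used for change from baseline, that some Week 0 tubes are in fact late, and that those tubes already carry drug effect. If all three are true, the guselkumab-placebo comparison is biased towards no effect by an amount that cannot be stated from the documents. The mRSS analysis, the proof-of-concept criterion, the secondary endpoints and safety are not affected. This is a minor, inexpensive correction to exploratory sampling.

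**What to change.** 1. Restrict footnote d to the EDTA tube for DNA.
2. Add to Table 1 that the Week 0 PAXgene tube is drawn before the first dose.
3. In the biomarker analysis, use the recorded collection and dosing times so that only samples taken before the first dose count as baseline. A Week 0 tube timed after it has no baseline value.

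This takes two footnote edits and one analysis sentence, with no additional samples. The downside is that a few late RNA tubes will be recorded as deviations, or their participants will drop out of the change-from-baseline summary. A matching pre-dose note for the Week 0 serum biomarkers, PBMCs and skin biopsy would be an optional clarification. If the manuals already contain it, a cross-reference is enough.
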